1.4 Study Design

This is multi-center two stage phase 2 study to evaluate the clinical activity of retifanlimab in patients with unresectable or metastatic ASQ. This study will enroll subjects who have progressed after at least 1 prior chemotherapy regimen, have been deemed unfit for cytotoxic chemotherapy or who have refused cytotoxic chemotherapy. The primary endpoint of this study will be disease control rate (DCR) at 4 months following the start of treatment using RECIST 1.1. Up to 25 subjects will be enrolled to target 21 evaluable patients.

The study will consist of a screening period (within 21 days of first dose), a treatment period per the table below (**Section 10**), and a follow-up period. Subjects will receive a baseline biopsy and then be treated with the anti-PD1 antibody retifanlimab every 4 weeks. After 2 doses (8 weeks), subjects will be assessed for response with imaging and laboratory tests and receive another research biopsy. For patients with stable disease or tumor response and clinical benefit, retifanlimab will be continued until disease progression or unacceptable toxicity. Patients will be evaluated radiographically after every 2 doses of retifanlimab (every 8 weeks). Subjects will come

to the clinic for dosing and assessments on Day 1 of each cycle. Assessment will consist of 1) physician evaluation to assess symptoms of tumor response or progression and potential drug related toxicity, 2) cross sectional imaging (CT scans), 3) CA19-9 blood levels. Additional visits for safety and immune monitoring follow-up will occur per the study calendar in **Section 10**.

No dose escalations or reductions are allowed. Enrollment will continue until 21 subjects have received at least one dose of retifanlimab and completed one cycle of therapy. The null hypothesis that the DCR 4 months following the start of treatment is 5% will be tested against a one-sided alternative (DCR of 30%).

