Complete unacceptable toxicity criteria can be found in **Section 5.7**. At the investigator's discretion, subjects may receive additional cycles of treatment if they are clinically stable and meet dosing eligibility criteria. All subjects may continue in the treatment period until the criteria in **Section 5.9** are met. Subjects may continue on treatment with radiographic disease progression if clinically stable and investigator believes the treatment is providing benefit. Subjects will be considered in the treatment period until 28 days after the last dose of study drug.

Patients who have a confirmed complete response by two scans ≥ 4 weeks apart and who have been on retifanlimab treatment for at least 6 months may discontinue retifanlimab treatment at the discretion of the investigator after receiving at least two doses beyond the initial determination of CR. Patients with SD, PR or CR that received at least 24 months of retifanlimab may also discontinue retifanlimab at the discretion of the investigator. Retifanlimab may be resumed upon disease recurrence or progression in these patients. Criteria and procedures for retreatment are described in Sections 5.9.2 and 10.0.

After completion of treatment and end of treatment (EOT) visit assessments, all subjects, including those who did not receive treatment, will continue to be followed every three months (± 2 weeks) by telephone, e-mail, or optional clinic visit until death, withdrawal of consent, or closure of study. Subjects will also be contacted at 90 days (+14 day reporting window) from the last dose of therapy. Information on survival and new cancer therapies will be collected. All subjects who discontinue study treatment should continue to be monitored for disease status by radiologic imaging every two months (± 2 weeks) until: 1) the start of a new antineoplastic therapy (information of the new cancer therapy will be collected), 2) disease progression, 3) death, 4) withdrawal of consent, or 5) the close of the study, whichever occurs first. All subjects will be followed after their last dose of study drug for the development of adverse events (AEs) and serious adverse events (SAEs) as described in **Section 7.5**.

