5.9 Criteria for Removal from Treatment

The reason for study removal and the date the subject was removed will be documented in the CRF.

A subject will be discontinued from the trial for any of the following reasons:

• The subject or legal representative (such as a parent or legal guardian) withdraws consent for participation in the study.

A subject must be discontinued from treatment (but may continue to be monitored in the post-treatment follow-up portion of the trial) for any of the following reasons:

- The subject or legal representative (such as a parent or legal guardian) withdraws consent for treatment.
- Intercurrent illness that prevents further administration of treatment,
- Unacceptable toxicity (see **Section 5.6**). Exceptions for treatment discontinuation are listed in **Section 5.6**,
- Disease progression as defined in **Section 5.9.1**,
- Severe or life-threatening retifanlimab-related AE(s) (see Section 6.2),
- Need for >2 dose delays due to the same drug-related toxicity as per the dose delay guidelines (see **Section 6.2**),
- If, in the opinion of the Investigator, a change or temporal or permanent discontinuation of therapy would be in the best interest of the subject.
- Noncompliance with trial treatment or procedure requirements,
- Subject is lost to follow-up, or
- Subject becomes pregnant.

A subject may, at the discretion of the Investigator, be discontinued from treatment (but may continue to be monitored in the post-treatment follow-up portion of the trial) if they have:

- Completed 6 months of treatment with retifanlimab and has a complete response (CR) by at least two scans ≥ 4 weeks apart AND have received at least two doses of retifanlimab beyond the initial determination of CR.
- Completed 24 months of treatment with retifanlimab and has a response of stable disease, partial response, or complete response at the time of discontinuation

Note: time on treatment is calculated from the date of first dose.

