5.9.1 Disease Progression

Retifanlimab is expected to trigger immune-mediated responses, which require activation of the immune system prior to the observation of clinical responses. Such immune activation may take weeks to months to be evident. Some subjects may have objective volume increase of tumor lesions or other disease parameters within weeks following the start of immunotherapy. Such subjects may not have had sufficient time to develop the required immune activation or, in some subjects, tumor volume or other disease parameter increases may represent infiltration of lymphocytes into the original tumor. In conventional studies, such tumor volume or relevant laboratory parameter increases during the first 2-4 months of the study would constitute disease progression and lead to discontinuation of imaging to detect response, thus disregarding the potential for subsequent immune-mediated clinical response.

Subjects will be permitted to continue with treatment beyond initial RECIST 1.1 defined PD as long as they meet the following criteria:

- Investigator-assesses that the patient is not clinically deteriorating, and
- Subject is tolerating study drug.

The assessment of lack of deterioration should take into account whether the subject is clinically stable or if they unlikely to receive further benefit from continued treatment. The following criteria need to be taken into consideration:

- No significant decline in ECOG performance status.
- Absence of rapid progression of disease or of progressive tumor at critical anatomical sites (e.g., cord compression) requiring urgent alternative medical intervention.

All decisions to continue treatment beyond PD must be discussed with the IND Sponsor and documented in the study records.

Tumor assessments will be made using RECIST 1.1 (**Appendix B**) and iRECIST (**Appendix C**).

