13.2 Data and Analysis Plan

Analysis of Primary Endpoint

The primary endpoint of the study will be disease control (DC) at four months using RECIST 1.1. DC is defined as complete response, partial response and stable disease at 4 months, per RECIST 1.1. Disease control rate (DCR) will be estimated as the proportion of patients who achieve DC at 4 months, along with 95% confidence interval

Analysis of Secondary Clinical Endpoint

The objective response rate defined as the proportion of response evaluable subjects who have a complete response (CR) or partial response (PR) using RECIST 1.1 criteria at any time during the study. The evaluable population includes all subjects who have completed at least one dose of retifanlimab and have received at least one follow-up scan or discontinue due to toxicity or clinical progression prior to post-baseline tumor assessments. Response rate will be reported with exact 95% confidence interval.

Progression-free Survival (PFS) is defined as the time from cycle 1, day 1 of retifanlimab until first documented local progression or death due to any cause. Disease progression will be assessed using RECIST (version 1.1) and/or documented clinical progression as assessed by the treating provider. Due to the expectation that some patients may experience delayed clinical responses to therapy, patients with disease progression by radiographic imaging or laboratory parameters during a 12-week evaluation period but without rapid clinical deterioration or significant change in performance status that requires additional immediate therapy may continue to receive treatment on study. Subjects that meet the above criteria and continue on study therapy must discontinue treatment upon documentation of disease progression on the second scan. The date of progression will be backdated to the time of first RECIST criteria progression. Tumor assessments will be made using RECIST 1.1 and immune RECIST (iRECIST). Individuals will be censored at the date of the last scan prior to initiation of an alternative therapy for PFS if no event occurs before the start of the alternative therapy.

PFS will be summarized descriptively using the Kaplan-Meier method. Analysis of PFS will be restricted to evaluable individuals who complete at least one dose of retifanlimab.

Analysis of Safety Endpoints

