On the confirmatory imaging, the participant will be classified as progression confirmed (with an overall response of iCPD), or as showing persistent unconfirmed progression (with an overall response of iUPD), or as showing disease stability or response (iSD/iPR/iCR).

Confirmation of Progression

Progression is considered confirmed, and the overall response will be iCPD, if ANY of the following occurs:

- Any of the factors that were the basis for the initial iUPD show worsening
 - \circ For target lesions, worsening is a further increase in the sum of diameters of ≥ 5 mm, compared to any prior iUPD time point
 - For non-target lesions, worsening is any significant growth in lesions overall, compared to a prior iUPD time point; this does not have to meet the "unequivocal" standard of RECIST 1.1
 - o For new lesions, worsening is any of these:
 - An increase in the new lesion sum of diameters by ≥ 5 mm from a prior iUPD time point
 - Visible growth of new non-target lesions
 - The appearance of additional new lesions
- Any new factor appears that would have triggered PD by RECIST 1.1

Persistent iUPD

Progression is considered not confirmed, and the overall response remains iUPD, if:

- None of the progression-confirming factors identified above occurs AND
- The target lesion sum of diameters (initial target lesions) remains above the initial PD threshold (by RECIST 1.1)

Additional imaging for confirmation should be scheduled 4 to 8 weeks from the scan on which iUPD is seen. This may correspond to the next visit in the original visit schedule. The assessment of the subsequent confirmation scan proceeds in an identical manner, with possible outcomes of iCPD, iUPD, and iSD/iPR/iCR.

Resolution of iUPD

Progression is considered not confirmed, and the overall response becomes iSD/iPR/iCR, if:

- None of the progression-confirming factors identified above occurs, AND
- The target lesion sum of diameters (initial target lesions) is not above the initial PD threshold.

The response is classified as iSD or iPR (depending on the sum of diameters of the target lesions), or iCR if all lesions resolve.

In this case, the initial iUPD is considered to be pseudo-progression, and the level of suspicion for progression is "reset". This means that the next visit that shows radiographic progression,

whenever it occurs, is again classified as iUPD by iRECIST, and the confirmation process is repeated before a response of iCPD can be assigned.

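### Section 13.2 requires a stop at progression on the second scan and refers to an undated 12-week window, while Sections 1.4 and 5.9.1 permit continued treatment after progression with neither limit

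*Combined protocol and SAP*

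**What the plan says.** Five places in the combined protocol and SAP bear on treatment after progression.

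- **Section 13.2 (PFS analysis).** Permission to continue is given to "patients with disease progression by radiographic imaging or laboratory parameters during a 12-week evaluation period" who are not deteriorating rapidly. Those who continue "must discontinue treatment upon documentation of disease progression on the second scan". For analysis, "The date of progression will be backdated to the time of first RECIST criteria progression".
- **Section 1.4.** For patients with stable disease or response and clinical benefit, "retifanlimab will be continued until disease progression or unacceptable toxicity". Later the same section says: "Subjects may continue on treatment with radiographic disease progression if clinically stable and investigator believes the treatment is providing benefit".
- **Section 5.9.** The list of mandatory reasons to stop treatment includes "Disease progression as defined in" Section 5.9.1.
- **Section 5.9.1.** "Subjects will be permitted to continue with treatment beyond initial RECIST 1.1 defined PD as long as they meet the following criteria": no clinical deterioration in the investigator's assessment, and tolerance of the drug. Each such decision must be discussed with the IND sponsor and documented. No scan or date is named at which treatment must end.
- **Appendix C.** At RECIST 1.1 progression the investigator decides, using the 5.9.1 criteria, whether to treat until repeat imaging, which follows 4 to 8 weeks later. If the second scan is still above the progression threshold without further worsening, the status stays iUPD (unconfirmed progression) and more imaging is scheduled: "The assessment of the subsequent confirmation scan proceeds in an identical manner, with possible outcomes of iCPD, iUPD, and iSD/iPR/iCR". No stop is stated, even at iCPD (confirmed progression).

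**The concern.** A mandatory stop appears in the statistical section and is missing from the sections that govern treatment. Staff working from Section 5.9.1 and staff working from Section 13.2 would handle the same patient differently, and no passage says which takes precedence.

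The choice affects several results. Section 13.4 counts unacceptable adverse events occurring at any time during treatment, so the rule changes the exposure that feeds the Bayesian stopping guideline. Section 7.5.1 collects adverse events to 28 days after the last dose, so it also changes the collection period. The iRECIST versions of DCR, ORR, PFS and DOR depend on who stays on drug after unconfirmed progression. OS may depend on it too.

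**Working it through.** **1. The primary design, to see whether it is touched.** Inputs from Section 13.1: 7 patients in stage 1, stop if none has disease control; 21 in total, reject at 3 or more; rates 5% and 30%. With X ~ Bin(7, p) and Y ~ Bin(14, p),

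P(reject) = P(X=1)·P(Y≥2) + P(X=2)·P(Y≥1) + P(X≥3).

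- p = 0.05: 0.2573 × 0.1530 + 0.0406 × 0.5123 + 0.0038 = 0.0639 (stated 0.064). Early stopping: 0.95^7 = 0.698 (stated 70%).
- p = 0.30: 0.2471 × 0.9525 + 0.3177 × 0.9932 + 0.3529 = 0.9038 (stated 90%).

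The plan's figures reproduce. They do not depend on the continuation rule: Table 6 in Appendix C says that under RECIST 1.1 a CR, PR or SD cannot follow progression, so a patient who has progressed is not a disease-control success whether or not treatment continues. PFS is dated at the first RECIST progression under every rule.

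**2. Scan timing.** Section 10, footnote 13: scans every 8 weeks ± 1 week from first treatment, so weeks 7–9, then 15–17. Section 13.2 gives no start for its 12 weeks; I assume first dose.

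- 9 ≤ 12 < 15, so only the first scheduled scan falls inside the window.
- A repeat scan 4 to 8 weeks after progression at week 7, 8 or 9 falls at weeks 11–15, 12–16 or 13–17.

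**3. Three clinically stable patients who tolerate the drug.** For Section 1.4, assume also that the investigator sees benefit.

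| Patient | Section 13.2 | Sections 1.4 (later statement) and 5.9.1 | Appendix C |
|---|---|---|---|
| A. Progression at week 8, target-lesion sum up a further 5 mm or more on the second scan | Must stop | May continue | iCPD; no stop stated |
| B. Progression at week 8, second scan still above the threshold but no worse | Must stop if progression means RECIST 1.1 PD; not if it means iCPD; not defined | May continue | Stays iUPD; more imaging; no dosing instruction |
| C. First progression at week 16 | Not addressed, if the 12 weeks run from first dose | May continue | Investigator decides under 5.9.1, until repeat imaging |

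Patient A gives a direct contradiction on either meaning of progression. Patient B shows an undefined term. Patient C shows a silence. The earlier statement in Section 1.4, read alone, would stop all three at first progression. Section 5.9 does not settle the matter, because its cross-reference leads to criteria for continuing and not to a stopping point.

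**4. How many patients.** This cannot be derived. The design rates imply that 1 − 0.30 = 70% to 1 − 0.05 = 95% of patients lack disease control at 4 months, but that group includes deaths, toxicity and clinical decline. The conflict reaches only those who are stable, continue, and again show progression on a second scan. The silence reaches those who first progress late.

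**The case against.** The best defence is that the passages can be read together. Section 5.9.1 speaks of initial RECIST 1.1 progression and 5.9 makes progression a mandatory stop, so 13.2 might be supplying the later limit. The sponsor must also discuss every decision to continue, which is a central check. The effect is confined to exposure, safety counts and exploratory endpoints.

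Part of this stands. The sponsor step reduces variation between sites, but it does not tell the sponsor which passage governs. The harmonised reading is possible, but nothing states it: Section 1.4 has no such limit, and 5.9 does not refer to 13.2.

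Four stronger readings are tempting, and the documents do not support them.

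- *Section 13.2 caps treatment past progression at 12 weeks.* The 12 weeks describe when progression is seen. If they run from first dose, the second scan that triggers the stop usually falls at or after week 12, so the window cannot also be a cap.
- *Section 13.2 forbids continuation after later progression.* It is silent on later progression, and 5.9.1 may fill the gap.
- *Appendix C lets the patient with persistent iUPD stay on drug.* It classifies scans, schedules imaging and defers to 5.9.1. It gives no dosing permission for that patient.
- *Most patients will be caught, given the 1.5-month median PFS in Section 13.1.* That figure is from metastatic PDAC, and the same section says there are no reliable historical data in ASQ. It also describes first progressions, not the smaller group the conflict reaches.

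**Conclusion.** The inconsistency is real and should be corrected. The firm part is patient A, who has opposite instructions under 13.2 and under 1.4 and 5.9.1 without any added assumption about criteria or dates. Two lesser gaps go with it: second-scan progression is not defined as RECIST 1.1 PD or iCPD, and the 12-week window has no start. The week-16 silence holds only if that window runs from first dose.

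The primary RECIST 1.1 DCR, its type I error and power, and backdated PFS do not change. Drug exposure, the on-treatment count of unacceptable toxicities and the exploratory iRECIST endpoints do depend on the rule, and OS may. The number of patients affected is unknown. I take no view on which rule is right.

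**What to change.** The sponsor and investigators should reconcile Sections 1.4, 5.9, 5.9.1 and 13.2 and Appendix C into one rule for treatment after RECIST progression, stated once and cross-referenced from the other places. The reference from 5.9 should then lead to an actual stopping point. If the window and the second-scan wording are kept, the rule should give the start of the window, say what applies to progression outside it, and say whether second-scan progression means RECIST 1.1 PD or iCPD. Section 13.2 should be limited to how progression is dated for analysis.

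The cost is protocol wording. No patients, scans or procedures are added, and the sample size does not change.

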11. STUDY ENDPOINTS

11.1 Primary Endpoint

The primary endpoint is DCR at 4 months following the start of treatment with retifanlimab, which is defined as the proportion of subjects with PR or CR or stable disease according to RECIST 1.1 following 4 months from the start of therapy. Subjects who discontinue due to toxicity prior to post-baseline tumor assessments will be evaluable and considered treatment failures. Otherwise, subjects who discontinue or do not have any post-baseline scans for other reasons including withdrawal of consent or being lost to follow-up prior to C2D1 will be replaced and not included in the primary efficacy analysis.

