11.2 Secondary Endpoints

The secondary endpoints are as follows:

- ORR is defined as the proportion of subjects with PR or CR according to RECIST 1.1. Subjects who discontinue due to toxicity or clinical progression prior to post-baseline tumor assessments will be considered as non-responders. Otherwise, subjects who discontinue or do not have any post-baseline scans for other reasons including withdrawal of consent or being lost to follow-up prior to C2D1 will be replaced and not included in the primary efficacy analysis.
- Progression-free survival (PFS) is defined as the number of months from the first
 dose of retifanlimab to radiographic disease progression (PD or relapse from CR
 as assessed using RECIST 1.1 criteria), documented clinical progression as
 assessed by the treating provider, or death due to any cause. PFS will be censored
 at the date of the last scan for subjects without documentation of disease
 progression at the time of analysis.
- Safety assessed by the following measures:
 - Number of patients who have grade 3 or above drug-related toxicities
 - Frequency of drug-related toxicity by grade
 - Retifanlimab-related infusion reactions
 - Immune-related AEs
 - Unacceptable toxicities
 - Vital signs: BP, pulse, temperature
 - Physical examination
 - Changes in ECG readings
 - Clinical hematology: complete blood count (CBC) with differential ANC,
 ALC, AEC, and platelet count
 - Clinical serum chemistry: sodium, potassium, chloride, bicarbonate, glucose, blood urea nitrogen (BUN), creatinine, lactate dehydrogenase (LDH), ALT, AST, alkaline phosphatase, lipase, bilirubin (total), total protein, albumin, calcium, magnesium and phosphate

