11.3 Exploratory Endpoints

- OS, DOR, TTP.
 - Overall survival (OS) is defined as the number of months from the first dose of retifanlimab until death or end of follow-up (OS will be censored on the date the subject was last known to be alive for subjects without documentation of death at the time of analysis).
 - Duration of Response (DOR) is defined as the number of months from the first documentation of a response to date of disease progression.
 - Time to-progression (TTP) is defined as the number of months from the first dose of retifanlimab to the date of documented disease progression (PD or relapse from CR as assessed using RECIST 1.1 criteria). It differs from PFS in that it does not include death in the definition of an event. TTP will be censored at the date of the last scan for subjects without documentation of disease progression at the time of analysis.
 - Disease control rate (DCR) is defined as the proportion of subjects with complete response, partial response and stable disease
- Disease control rate, objective response rate, progression-free survival, and duration of response measured by iRECIST
- Immune subset analyses by IHC, next generation sequencing and gene expression profiling of tumor tissue
- Immune subset analyses in PBMCs including effector, helper, and regulatory T cells, NK cells, and macrophages
- Circulating cytokine analysis in patient sera
- Immune checkpoint analysis by IHC and gene expression profiling
- Tumor marker kinetics measured by change in serum CA19-9 concentrations from baseline

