13. STATISTICAL CONSIDERATIONS

13.1 Study Design/Endpoints

Sample Size calculation and justification

Simon's two-stage optimal design will be used ¹⁸. The null hypothesis that the true disease control rate at 4 months is 5% will be tested against a one-sided alternative of 30% disease control rate at 4 months. In the first stage, 7 patients will be accrued. If there are zero patients with disease control by 4 months, the study will be stopped. Otherwise, 14 additional patients will be accrued for a total of 21 patients. The null hypothesis (disease control rate of 5%) will be rejected if 3 or more patients with disease control at 4 months are observed in stage 1 and 2 combined. This design yields a type I error rate of 0.064 (target type I error 0.1) and power of 90% when the true disease control rate is 30%. The probability of stopping the trial early for futility is 70% if the true DCR is 5%.

We plan to enroll 25 subjects to ensure 21 would be evaluable for DCR. As this is a rare tumor subtype patients will be recruited at several sites including Johns Hopkins Hospital, Memorial Sloan Kettering Cancer Center and the Mayo Clinic. We do not anticipate any difficulties in trial enrollment. We expect an accrual rate of at least 2 patients per month across the sites, completing trial enrollment in 12 months.

Patients are evaluable for DCR if they receive at least one dose of retifanlimab, and have at least one post-baseline tumor assessments or discontinue due to toxicity or clinical progression prior to post-baseline tumor assessments. The study plans to enroll 25 subjects to ensure 21 would be evaluable for the primary efficacy endpoint.

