The safety analysis will be performed in all subjects who receive at least one dose of study drug. A baseline measurement and at least 1 laboratory or other safety-related measurement obtained after at least 1 dose of study treatment may be required for inclusion in the analysis of a specific safety parameter (e.g., lab shifts from baseline). A complete list of all AE data will be provided along with an assessment of NCI CTCAE grade and relationship to study drug. The incidence of AEs will be tabulated by subgroups of interest (e.g. grade 3 or higher, organ class, relationship to study drug). For analyses at the individual level, the highest grade and relationship to study drug will be assumed if multiple events have occurred. Toxicity will be tabulated by type and grade and will be summarized with descriptive statistics. Other safety data will be assessed in terms of

physical examination, clinical chemistry, hematology, vital signs, and ECGs. Negative binomial regression and Cox proportional hazards models will be used to assess the rate of AE and time to first toxicity, respectively.

Exploratory Clinical Analysis

Overall survival is defined as the duration of time from start of study treatment to time of death. For subjects lost to follow-up or whose vital status is unknown, every effort will be made to determine the date such subjects were last known to be alive. Such efforts may include phone calls, certified mail, and the checking of public records. Subjects who are alive or lost to follow-up as of the data analysis cutoff date will be right-censored. The censoring date will be determined from the date the subject was last known to be alive.

OS will be summarized descriptively using the Kaplan-Meier method. Analysis of OS will be restricted to evaluable individuals who complete at least one dose of retifanlimab. Median event-free survival will be reported and the associated 95% confidence interval will be estimated.

DOR and TTP were defined in second 11.3.

Exploratory Biomarker Analysis

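### PFS and OS are limited to 'evaluable' subjects without saying which definition applies; if the response-endpoint definition is carried over, a treated death before the first scan can drop out of both curves

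*Combined protocol and SAP*

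**What the plan says.** Section 13.2 sets the PFS analysis set with "Analysis of PFS will be restricted to evaluable individuals who complete at least one dose of retifanlimab" and the OS set with "Analysis of OS will be restricted to evaluable individuals who complete at least one dose of retifanlimab". Neither sentence defines the first condition.

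Evaluability is defined only for the tumour-assessment endpoints. In the ORR paragraph of 13.2, "The evaluable population includes all subjects who have completed at least one dose of retifanlimab and have received at least one follow-up scan", with an exception for subjects who stop early because of toxicity or clinical progression. For DCR, Section 13.1 asks for one dose and that subjects "have at least one post-baseline tumor assessments or discontinue due to toxicity or clinical progression prior to post-baseline tumor assessments". Death is not among the exceptions in either place.

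Two other passages use related but different conditions. Section 1.4 says "Enrollment will continue until 21 subjects have received at least one dose of retifanlimab and completed one cycle of therapy". Section 11.1 names toxicity as the only pre-scan exception. It then says that those who "do not have any post-baseline scans for other reasons including withdrawal of consent or being lost to follow-up prior to C2D1 will be replaced"; the same rule covers early stops for such reasons, and these subjects stay out of the primary efficacy analysis.

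The endpoint definitions carry no such limit. In 11.2 and 13.2, death from any cause is a PFS event. In 11.3, "Overall survival (OS) is defined as the number of months from the first dose of retifanlimab until death or end of follow-up". The first on-study scan is due at 8 weeks, plus or minus 1 week (Section 10, note 13). The safety analysis in 13.2 uses everyone with at least one dose.

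**The concern.** A date of death is known without a scan, so neither PFS nor OS needs a scan-based restriction. Having a post-baseline scan depends partly on living long enough to have one. A survival curve limited to subjects with a scan therefore loses its earliest deaths, and later values can only rise. The trial has one arm, so no control group would share the distortion.

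The stake is limited to how two descriptive curves read. PFS is secondary and OS exploratory. Neither is tested, and neither enters the go/no-go rule. Because the word is undefined, however, the analysis set could be settled after the early deaths are known.

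**Working it through.** **1. Passages side by side.**

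| Place | Condition | Exceptions without a scan | Applies to |
|---|---|---|---|
| 13.1 | dose plus post-baseline assessment | toxicity, clinical progression | DCR |
| 13.2, ORR paragraph | dose plus follow-up scan | toxicity, clinical progression | ORR; phrased as the evaluable population in general |
| 11.1 | subjects without scans for other reasons are replaced | toxicity | primary efficacy analysis |
| 1.4 | one dose and one completed cycle | none | enrolment target |
| 13.2, PFS and OS sentences | 'evaluable' and one completed dose | not stated | PFS, OS |
| 11.2, 11.3 | none | none needed | PFS and OS definitions |

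Two readings are open:
- (a) 'Evaluable' carries the DCR/ORR definition. A subject is then lost if dosed, dead before the first scan, and without a recorded stop for toxicity or clinical progression.
- (b) 'Evaluable' means dosed, and nobody is lost.

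**2. The plan's own figures.** The plan gives no precision or power figure for PFS or OS. Its Simon design (stop at 0 of 7; reject at 3 or more of 21; 5% against 30%) was recomputed as the sum over x ≥ 1 of P(X1 = x) × P(X2 ≥ 3 − x), with X1 ~ Bin(7, p) and X2 ~ Bin(14, p). Type I error is 0.0639 (stated 0.064), power 0.904 (90%) and early stopping at 5% is 0.698 (70%). These reproduce and do not depend on the PFS/OS set.

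**3. Direction and minimum size under (a).** Take N = 25 dosed (planned enrolment, 13.1) and k removed deaths. Let n_i be the number at risk and d_i the deaths at the i-th death time. Removing one death at time d, with n_d at risk, multiplies every later Kaplan-Meier value by

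prod over earlier death times of [(n_i − 1 − d_i)/(n_i − d_i) × n_i/(n_i − 1)] × n_d/(n_d − 1).

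Because n_(i+1) ≤ n_i − d_i, this telescopes to at least n_1/(n_1 − 1) ≥ N/(N − 1). Repeating it k times gives at least 25/(25 − k), with equality when there is no earlier censoring. In 6,000 random censored data sets (62,701 ratios) none fell below this bound. Before the last removed death the curve can be slightly lower, for example 23/24 = 95.8% instead of 24/25 = 96.0%.

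**4. Values for assumed k, no censoring.** The documents give no early-death rate, so k is an assumption; k = 4 is an extreme.

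| k | 25/(25 − k) | 12 of 25 alive = 48% (exact 95% CI 28-69%) reads | 5 of 25 progression-free = 20% (7-41%) reads |
|---|---|---|---|
| 1 | 1.04 | 12/24 = 50% | 5/24 = 20.8% |
| 2 | 1.09 | 12/23 = 52% | 5/23 = 21.7% |
| 4 | 1.19 | 12/21 = 57% | 5/21 = 23.8% |

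**5. OS median.** With no earlier censoring, the median is the first death at which survival is 50% or less. That is the 13th of 25 with everyone included. Counted among the 25, it is the 13th, 14th and 15th death after removing k = 1, 2 and 4. As a scale only, assume exponential OS with median m = 5.65 to 6.8 months (the gemcitabine figures in 2.1).
- The 13th-to-14th gap is m/(12 ln 2) = 0.120m, or 0.68 to 0.82 months.
- The 13th-to-15th gap is (1/12 + 1/11) × m/ln 2 = 0.251m, or 1.42 to 1.71 months.

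**6. PFS median.** Simulation with n = 25: k deaths uniform over weeks 0-7, the rest with exponential progression of median 1.5 months (the pancreatic checkpoint-inhibitor trial cited in 13.1), detected at 8-weekly scans.
- With each scan moved by up to 1 week either way, the typical shift is 0, 1, 1 and 2 days for k = 1 to 4. The median is exactly unchanged in 100%, about 30%, about 31% and about 6% of runs.
- With scans at exactly 8-week intervals and no window, it is unchanged in 100%, 89%, 91% and 81%. In the remainder (0%, 11%, 9%, 19%) it jumps a whole scan interval.

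**The case against.** The benign reading has real support. The scan-based definitions are attached to DCR and to ORR. The PFS and OS definitions in 11.2 and 11.3 have no evaluability limit. The replacement rule sits in the DCR and ORR definitions and reaches only the primary efficacy analysis. The OS sentence stands in a different subsection from the ORR definition. Redundancy does not decide the matter: under (b) the word 'evaluable' adds nothing, but under (a) the words about one dose add nothing either, because the definition already requires a dose.

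The group is also narrow. Clinical progression needs no scan to be documented. Subjects who stop without progression continue to be imaged (5.12.2). Entry requires ECOG 0 or 1 and life expectancy above 3 months (3.1). For PFS, a subject without a post-baseline scan who starts another therapy and then dies adds no event under the 13.2 censoring rule, so omitting that subject matters only for OS.

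All of this stands, and it limits the size of the problem. It does not settle the reading: 13.2 speaks of the evaluable population without qualification, immediately before the PFS paragraph, and no passage says that a death before a scan stays in.

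A reader might infer that the plan excludes early deaths from PFS and OS, or that the reported survival will be materially inflated. The documents support neither. The first depends on a definition that the text does not attach to these endpoints; the second needs an early-death count that the documents do not give.

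**Conclusion.** The concern holds as an undefined analysis set with a one-directional risk. Under the definition used for DCR and ORR, a treated death before the first scan can be left out of endpoints that count death, and later survival values are then at least 25/(25 − k) times as high.

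The expected size is small. The number affected is unknown and possibly 0. For an assumed k = 1 neither median moves. For k = 2 the OS median moves by about 0.7-0.8 months (1.4-1.7 for k = 4), given exponential survival on the assumed scale and no earlier censoring. The PFS median typically moves by 0-2 days over k = 1 to 4 and occasionally by a whole scan interval. It would be wrong to say that the PFS median usually stays exactly put for k of 2 or more: that is true only if scans fall at exact 8-week intervals, which note 13 does not require. The illustrated survival percentages stay inside their confidence intervals, and the Simon decision is untouched. This is a cheap improvement to make before analysis and does not threaten the trial's main conclusion.

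**What to change.** In 13.2, replace both restricting sentences with: *PFS and OS will be analysed in all subjects who received at least one dose of retifanlimab.* This is the safety set. Moving from a completed to a received dose also brings in subjects whose first infusion was not finished, and the change should be declared.

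Then state the handling:
- OS: every death is an event; censoring at the date last known alive stays as written.
- PFS: a death before the first scan is an event on its date, unless alternative therapy started first.
- PFS without a post-baseline scan: censor at day 1 if there is no event, or if alternative therapy started before any event. This is an added convention. Section 13.2 censors at the last scan before the new therapy, which for such a subject would literally be the screening scan, before day 1.

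The evaluable set, with its definition written out, may be kept as a sensitivity analysis.

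The cost is two replaced sentences and a short handling rule. No new data are needed, because Section 1.4 already follows all subjects for survival. If the intention was all dosed subjects, little or nothing changes in the results; otherwise the estimates may be slightly less favourable.
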